**5.7 Adherence to the intervention**

A descriptive analysis of KMC provided to both arms will be conducted. The following will be calculated as indicators of adherence and presented in a table format: mean chronological age at first KMC contact; mean time since admission at first KMC contact; mean daily dose of KMC (h/day) for first 7 days since enrolment; mean daily dose of inpatient KMC, per number of days admitted. The proportion of patients transferred from the neonatal unit to the KMC unit for each arm will be described with mean (and standard deviations) chronological ages at admission. Individual patient data on the actual daily dose of in-patient KMC, up-to 28 days of age, will be represented for both control and intervention arms using heat maps and box plots. This will provide a visual representation of the intervention provided over the study period. The number and proportion of participants in the intervention arm who met KMC stopping criteria for clinical reasons will be described with reporting of reasons and mean age at time of stopping.

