### 8.2 Adverse events

See definitions, page 10, for general definition of AE. For the purposes of this study, it will include but is not restricted to the following:

- Deterioration in clinical stability, as per study definitions of stability
- Clinical deterioration as per adapted PSBI criteria
- Any other deterioration needing change in management, out-with routine management
- Abnormal investigation
- Detection of congenital malformation not apparent at time of recruitment

AE will be pre-defined and all AE will be recorded in the SMR, Adverse Event Log and eCRF and reported as below.

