## **9 DISCONTINUATION CRITERIA**

### **9.1 Participant's premature termination of intervention**

#### **9.1.1 Criteria for temporary with-drawal from intervention arm**

Participants will stop the intervention if any of the following criteria apply:

“Stopping criteria”:

1. Severely unstable for >10 minutes if:
  - ✓ SPO2<88% in oxygenAND ≥1 of:
  - ✓ Respiratory rate <20 or > 100 breaths/min
  - ✓ Severe chest in-drawing
  - ✓ Apnoea needing bag-valve-mask ventilation
  - ✓ HR <100 or >200 beats/min

OR CPAP is required on clinical grounds as per Standardised Preterm Management Criteria

2. Any other condition which precludes continuous skin-to-skin contact
  - a. Severe jaundice needing immediate management
  - b. Severe anaemia needing blood transfusion
  - c. Seizures
  - d. Severe abdominal distension
  - e. Omphalitis or infection of the umbilical cord
  - f. Apnoea needing bag-valve-mask ventilation
  - g. Widespread skin infection of baby or caregiver providing skin-to-skin contact
  - h. Mother or caregiver not available or willing to do continuous skin-to-skin contact

Protocol #: 1

---

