### **6.5 Harms**

Adverse events and SAEs will be listed and defined with reference to standardised criteria where appropriate. The methods used for data collection and attribution of events will be described.

The number and proportion of participants with an SAE (life-threatening event; risk of disability; re-admission to hospital or prolonged hospital stay >28d) will be presented for both arms. Death will not be included as this is the primary outcome of the trial.

A detailed analysis of blood glucose levels over the first 24h of study participation will be performed as a proxy indicator of disturbance to the IV fluid administration. This will involve number and proportion of participants with hypoglycaemia or hyperglycaemia at defined time points as well as mean glucose level at baseline, 12h and 24h. The significance level will be calculated using chi squared or Fisher's exact tests for categorical variables. Continuous variables will be compared using Student's *t*-test or nonparametric tests, when appropriate. The appropriate effect size will be presented, using risk ratios for binary outcomes and difference between means for continuous data.

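### Clinical stopping events are reported for one arm only, and five of the stopping reasons have no planned between-arm comparison

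*SAP*

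**What the plan says.** **Stopping events.** SAP 5.7, on adherence, gives most of its indicators for both arms, but this one for a single arm: "The number and proportion of participants in the intervention arm who met KMC stopping criteria for clinical reasons will be described", together with reasons and mean age. The criteria are in Protocol 9.1.1, headed "Criteria for temporary with-drawal from intervention arm". Item 1 opens "Severely unstable for >10 minutes if" and also covers a need for CPAP. Item 2, "Any other condition which precludes continuous skin-to-skin contact", lists severe jaundice, "Severe anaemia needing blood transfusion", seizures, severe abdominal distension, omphalitis, "Apnoea needing bag-valve-mask ventilation", widespread skin infection of baby or caregiver, and caregiver unavailability.

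**Harms.** SAP 6.5 says "Adverse events and SAEs will be listed and defined with reference to standardised criteria where appropriate". It then promises numbers and proportions by arm for SAEs, grouped as life-threatening events, risk of disability, and re-admission or prolonged stay. Death is left out because it is the primary outcome. Risk ratios and mean differences are mentioned at the end of the paragraph on blood glucose; no effect measure is tied to the SAEs.

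**Recording.** Protocol 8.2 counts as AEs, among others, "Deterioration in clinical stability, as per study definitions of stability" and deterioration on the adapted PSBI criteria. It requires all AEs to be logged and entered in the eCRF, without restriction by arm.

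**The concern.** Apart from caregiver skin infection and caregiver unavailability, the stopping criteria describe the state of the baby, and control babies can reach them too. A count from one arm has no comparator. A high figure could be taken as harm from skin-to-skin contact or dismissed as the course of small, unstable babies, and the count itself cannot decide between the two.

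Safety is Objective 3, and Protocol 14.3.1.a accepts that the safety profile of early contact in unstable babies in this kind of setting is less well established. If conditions recorded in both arms are not tabulated in both, part of the randomised safety evidence goes unused.

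**Working it through.** **1. Stopping reasons against planned comparisons.** Protocol 9.1.1 is set beside the SAE list in Protocol 8.3 and the analyses in SAP 6.5.

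| Reason in Protocol 9.1.1 | Named SAE in Protocol 8.3? | Planned between-arm figure |
|---|---|---|
| 1 Severe instability or CPAP need | Yes, life-threatening | Within pooled SAE category |
| 2f Apnoea needing bag-valve-mask ventilation | Yes, if not fatal | Within pooled SAE category |
| 2a Severe jaundice | Yes, if phototherapy or exchange transfusion is needed | Within pooled SAE category |
| 2b Anaemia needing transfusion | No | None |
| 2c Seizures | No | None |
| 2d Severe abdominal distension | No | None |
| 2e Omphalitis or cord infection | No | None |
| 2g Widespread skin infection, baby | No | None |
| 2g caregiver part, 2h | Not a condition of the baby | Not applicable |

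Some cases in the five uncovered rows could become SAEs by another route, such as clinician judgement of a life-threatening situation, suspected meningitis or encephalopathy. That does not amount to a planned comparison of the condition.

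**2. Do other outcomes cover the five?** Suspected late-onset infection is defined by pallor, lethargy, jaundice, apnoea or hepatomegaly, so none of the five qualifies by itself. The aSCRIP score, hypothermia, heart rate, saturation and glucose analyses concern the first 24 hours, whereas the intervention runs to discharge.

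**3. Can the SAE table supply the missing control count?** Not exactly. The Protocol definitions set severe instability by low saturation for more than 5 minutes plus another sign. Item 1 of 9.1.1 uses more than 10 minutes. The two counts need not match until these passages are reconciled.

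**4. The plan's own sample size.** Inputs from SAP 3.3: control mortality 0.48; 30% relative reduction, so 0.48 × 0.70 = 0.336; power 80%; alpha 0.05 (two-sided assumed). Mean proportion 0.408, difference 0.144.

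- n = [1.960 × √(2 × 0.408 × 0.592) + 0.8416 × √(0.48 × 0.52 + 0.336 × 0.664)]² / 0.144² = 181.7
- With continuity correction: (181.7/4) × [1 + √(1 + 4/(181.7 × 0.144))]² = 195.3, so 196 per arm and **392 in total**, as stated.

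**5. What 196 per arm gives for a harm event.** The control rates are assumptions, because the documents give none. The 95% half-width for the risk difference at equal rates is 1.96 × √(2p(1−p)/196). The detectable rate is for 80% power, two-sided 5%, with no continuity correction and no allowance for twin clustering.

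| Assumed control rate | Half-width, points | Detectable rate | Risk ratio |
|---|---|---|---|
| 5% | 4.3 | 13.1% | 2.6 |
| 10% | 5.9 | 20.1% | 2.0 |
| 20% | 7.9 | 32.5% | 1.6 |
| 30% | 9.1 | 43.7% | 1.5 |
| 40% | 9.7 | 54.1% | 1.35 |

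Check of the first row: the null SE is √(2 × 0.0905 × 0.9095/196) = 0.0290 and the alternative SE is √((0.05 × 0.95 + 0.131 × 0.869)/196) = 0.0287. Then (0.081 − 1.96 × 0.0290)/0.0287 = 0.84, which is 80% power.

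**6. Why deaths must stand alongside.** On the design assumptions, mortality differs by 14.4 points, or 0.144 × 196 ≈ 28 babies. If the intervention works, about 28 more babies in that arm stay alive and at risk of a later non-fatal event. Crude proportions alone would then count against it.

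**The case against.** The strongest reply is that SAP 5.7 concerns adherence. Controls have no allocated early contact to stop, so a one-arm count is the natural way to explain interruptions, and the SAP does not call it harm. This stands, and the count should stay where it is.

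A reader might infer from the one-arm count that the trial cannot separate harm from natural course. The documents do not support that. The most serious stopping events are SAEs shown for both arms. Mortality, time to death, suspected infection, 24-hour physiology and glucose are also randomised comparisons. Protocol 2.1 ties Objective 3 to cardio-respiratory stability at 24 hours, which is one of them.

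A reader might also take the 23% in Protocol 1.1 (death or severe instability during screening) as the background rate. It is a barrier to recruitment before enrolment: babies who died or remained severely unstable at the 3-hour assessment were not enrolled. Nor should detectability at a high pooled rate, such as the 30% row above, be credited to the fix, because it mixes in events already counted as SAEs.

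The sentence on listing AEs can fairly be read as being about definitions. The SAP is then silent on non-serious AE tables rather than excluding them. Silence still leaves no specified comparison.

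It is also true that the documents do not name omphalitis, skin infection or distension as harms of skin-to-skin contact. The case for tabulating them is completeness of a randomised safety comparison, without any presumed causal link.

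Finally, ascertainment may differ by arm. The trial is unblinded, assessment for withdrawal applies to the intervention arm (Protocol 6.1.3), and review becomes weekly after transfer to the KMC unit (Protocol 6.1.2). This limits what the table can show and has to be stated with it.

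**Conclusion.** The point holds as a gap in harm reporting. The stopping count has no control figure, the three main stopping events are compared only within pooled SAE categories, and five further conditions have no planned between-arm comparison. No primary or secondary outcome and no sample size figure is affected.

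Its size in event terms cannot be given, because the documents contain no rates for the five conditions. At an assumed 5% control rate, only a rise to about 13% would be detectable with 80% power, and the risk difference would carry a half-width of about 4 points. These figures assume 196 babies per arm with complete data and ignore twin clustering, which would normally widen them. The benefit is an interpretable and complete safety description; small excesses would still be missed. Cheap improvement.

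**What to change.** - **SAP 5.7:** keep the intervention-arm count and label it as adherence only, not as evidence of harm.
- **SAP 6.5:** tabulate by randomised arm (a) SAEs by type, (b) non-serious AEs by type, and (c) the baby-level clinical conditions of Protocol 9.1.1: item 1 and items 2a to 2g, without caregiver skin infection. Use the AE log, daily reviews and treatment records.
- **Estimates:** give the number and proportion of babies with at least one event, with risk ratio, risk difference and 95% CI from the GEE approach of SAP 6.2. Where events are too few for the model, give counts with exact intervals. Show deaths by arm alongside.
- **Ascertainment:** restrict the main comparison to the inpatient period and footnote the unblinded detection, the one-arm withdrawal assessment and the weekly KMC-unit review. Length of stay is itself an outcome and may differ by arm, so report inpatient days next to the table.
- **Definitions:** reconcile the more-than-5-minute definition of severe instability with the more-than-10-minute stopping criterion, and state which each count uses. This is a request for comparable counting and implies no view on the clinical threshold.

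**Cost:** SAP wording and one or two tables, with no apparent new data collection. Convulsions and abdominal distension are on the adapted PSBI list in Protocol 6.1.3, and concomitant treatments are recorded under Protocol 3.5, which should identify transfusions. Recording of omphalitis and skin infection in controls is less explicit, so control counts for these two may be incomplete and should be marked so.

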## 6. Analysis of outcomes

### 6.1 Outcome definitions

Primary outcome:

All-cause mortality at 28d

Secondary outcomes:

1. Time from intervention/control procedures starting to death (days & hrs)
2. Mean cardio-respiratory stability at 24h of intervention (aSCRIP score)
3. Prevalence of hypothermia ( $T < 36.5^{\circ}\text{C}$ ) at 24h of intervention
4. Mean daily weight gain (g/day) at 28d
5. Proportion of infants exclusively breastfeeding at discharge
6. Mean duration of hospital admission (days & hours)
7. Incidence of clinically suspected infection after 3 days and by 28 days or latest follow up
8. Prevalence of neonatal intestinal carriage of ESBL-Klebsiella pneumoniae at 28d

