# 2 STUDY OBJECTIVES & OUTCOMES

## 2.1 Objectives

**Objective 1. To assess the effect of early continuous skin-to-skin contact on survival of hospitalised, mild-moderately unstable neonates weighing <2000g**

This will be achieved by measurement of the primary outcome of mortality at 28d and secondary outcomes of time to death..

**Objective 2. To assess the effect of early continuous skin-to-skin contact on other important clinical outcomes for hospitalised, mild-moderately unstable neonates weighing <2000g**

This will be achieved by measurement of the following secondary outcomes:

- Growth (weight)
- Duration of hospital admission

Protocol #: 1

---

- Suspected late onset infection

**Objective 3. To assess the safety of early continuous skin-to-skin contact in the hospital management of mild-moderately unstable neonates <2000g**

This will be achieved by measurement of the following secondary outcomes:

- Cardio-respiratory stability at 24h

**Objective 4. To explore causal pathways for the beneficial clinical effects of early continuous skin-to-skin contact compared to standard care in hospitalised, mild-moderately unstable neonates weighing <2000g**

This will be achieved by measurement of the following secondary process outcomes:

- Time to mortality
- Cardio-respiratory stability at 24h (early pathway)
- Hypothermia (early or late pathway)
- Exclusive breastmilk feeding at discharge (late pathway)
- Prevalence of intestinal ESBL-Klebsiella pneumoniae carriage (samples to be taken and stored, pending future funding)
- In addition and also as part of objective 4, carriage swab samples, environmental samples and blood/CSF culture isolates will be stored with the intention of undertaking the following work at a future stage, once additional funding is secured:
  1. Explore the effect of early skin-to-skin contact on neonatal intestinal/rectal microbiome, with comparison to maternal/caregiver microbiomes (16SrRNA)
  2. Describe the molecular epidemiology of ESBL-KP isolates, including clonal diversity and antibiotic resistance profile (whole genome sequencing)
  3. Compare neonatal carriage and invasive isolates with environmental isolates and maternal/caregiver carriage isolates to explore transmission of neonatal pathogens (whole genome sequencing)

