# **6 STUDY EVALUATIONS**

## **6.1 Clinical evaluations**

### **6.1.1 Evaluations during first 24h of intervention**

All subjects will have continuous cardio-respiratory monitoring with a Nonin 2500A pulse oximeter for minimum 24h after intervention/control procedures begin and continued until the subject is stable (definitions, page 10).

Manual auxiliary temperature will be taken 6hrly for the first 24h. The subjects will be reviewed every 6h for manual recording of the respiratory rate and breathing pattern and reviewed at least once by the study clinician during the initial 24h period. An adapted SCRAP score will be calculated post-hoc to quantify cardio-respiratory stability (Appendix 3). Blood sugar measurements will be measured every 6h, unless  $<2.6$  mmol/l in which case it will be measured 1hrly until 2 or more consecutive readings are in normal range (2.6 – 6.9 mmol/l).

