### APPENDIX III: ADAPTED SCRIP SCORE FOR MEASUREMENT OF CARDIO-RESPIRATORY STABILITY OUTCOME

		2 points	1 point	0 points
A	Cardiovascular stability:  Heart rate (beats per minute)	120 – 160 for 10 mins continuously	100 - 120 or 161 – 200 for >5 out of 10 mins	<100 or >200 continuously for >5 out of 10 mins
B	Respiratory stability:  Breathing pattern and respiratory rate (RR) (breaths per minute)	Regular breathing  And/or  RR 20 – 60 continuously for 10 mins	Irregular or periodic breathing with 1 or more pauses for <10 secs  And / or  RR 20 – 29 or 61 – 100 for >5 out of 10 mins	Irregular breathing with 1 or more pauses for >10 secs  And / or  Irregular breathing with 1 or more pauses for <10 seconds but which result in oxygen saturation <88%  Need for bag-valve-mask ventilation  And / or  RR <20 or >100 for >5 out of 10 mins
C	Oxygen saturation (%)	>88% continuously in room air for 10 mins	>88% continuously for >5 out of 10 mins in oxygen	<88% continuously for >5 out of 10 mins despite oxygen

[figure not shown]
Stable = 6

Mild – moderately unstable = 3 – 5

Severely unstable = 0 - 2

Protocol #: 1

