### 3.6 Timing of outcome assessments

Outcomes are assessed according to the following schedule:

Timing	Outcome
24h after study participation	

Cardio-respiratory stability (Mean adjusted SCRIp score)

Hypothermia (Prevalence of participants with temperature <36.5°C)

Daily whilst admitted to neonatal unit Weekly (day 7, 14, 21, 28) whilst admitted to KMC unit Ad-hoc reviews in event of clinical deterioration	

Time from start of study procedures to death (hours)

Incidence of clinically suspected infection from 3 – 28 days of age or latest follow-up

Day of discharge	

Exclusive breastfeeding

Duration of admission

Age 28 +/- 5 days	

Survival status (alive / died)

Weight gain (mean weight gain in g/day from baseline)

Prevalence of participants with intestinal carriage of ESBL-Klebsiella pneumoniae

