### **6.3 Missing data**

The amount of missing data is expected to be low (<5%) and a complete case analysis will be conducted.

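### The 24-hour stability and hypothermia outcomes leave out babies who die before the reading, so on their own they can, though need not, favour the arm with more early deaths

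*SAP*

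**What the plan says.** Objective 3 in Protocol 2.1 reads "To assess the safety of early continuous skin-to-skin contact in the hospital management of mild-moderately unstable neonates" weighing under 2000g. The single outcome listed beneath it is "Cardio-respiratory stability at 24h". The same outcome appears again under Objective 4 as an early causal pathway.

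SAP 6.1 makes this "Mean cardio-respiratory stability at 24h of intervention (aSCRIP score"), and SAP 3.6 times it, together with hypothermia prevalence, at "24h after study participation". Protocol 6.1.1 says that the adapted "score will be calculated post-hoc to quantify cardio-respiratory stability (Appendix 3"). That appendix adds three components scored 0 to 2 (heart rate, breathing, oxygen saturation), giving a range of 0 to 6. Its lowest band is "Severely unstable = 0 - 2", and it has no entry for death.

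On absent values, SAP 6.3 says: "The amount of missing data is expected to be low (<5%) and a complete case analysis will be conducted". SAP 5.4 covers withdrawal and loss to follow-up but not death. SAP 6.2 names models for continuous and binary outcomes without saying how a death before the measurement is handled. The only sensitivity analysis removes babies recruited in error.

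**The concern.** Death before the 24-hour reading differs from ordinary missing data. No value exists to recover, and on a safety question death is the worst result. Dropping these babies turns a randomised comparison into one between survivors, which sits awkwardly with the intention-to-treat statement in SAP 4.3.

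The loss may also differ by arm. The trial is powered for a 30% relative reduction in mortality, and its hypothesis includes early stabilisation. If skin-to-skin contact changes first-day deaths in either direction, the babies alive at 24 hours are no longer comparable between arms. Early harm could appear as better average stability, and rescue of the sickest babies could appear as worse stability. Because the score is the one outcome attached to the safety objective, a reader may take it at face value.

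**Working it through.** **1. The plan's own figure.** Inputs from SAP 3.3: control mortality 48%, relative reduction 30%, power 80%, alpha 0.05, 1:1 allocation. Intervention mortality is 0.48 × 0.70 = 0.336; the mean is 0.408 and the difference d is 0.144.

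n per arm = [1.960·√(2 × 0.408 × 0.592) + 0.8416·√(0.48 × 0.52 + 0.336 × 0.664)]² / 0.144² = (1.3622 + 0.5786)² / 0.020736 ≈ 181.7.

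With continuity correction: (181.7/4) × [1 + √(1 + 4/(181.7 × 0.144))]² ≈ 195.3, so 196 per arm and 392 in total. The plan's figure is reproduced (two-sided), so 48% and 33.6% are the right planning rates to use below.

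**2. What the rules do.** Take a baby who dies 10 hours after procedures start. There is no 24-hour aSCRIP (Protocol Appendix III) and no 24-hour temperature. SAP 5.4 does not apply. Under SAP 6.3 the baby is excluded from both analyses. With one score per baby, a random-effects model for twins cannot restore the missing value.

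**3. How many babies could be lost.** The documents do not give the share s of 28-day deaths that fall before the 24-hour reading, so s is an assumption. Missing share = 0.48·s in control, 0.336·s in intervention and 0.408·s overall.

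| s (assumed) | Control | Intervention | Overall |
|---|---|---|---|
| 10% | 4.8% | 3.4% | 4.1% |
| 20% | 9.6% | 6.7% | 8.2% |
| 30% | 14.4% | 10.1% | 12.2% |

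Deaths alone reach the SAP's 5% when s = 0.05/0.408 = 12.3%.

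The only timing data are in Protocol 1.1: a median age at death of 3d 2h (74 hours) among 14 deaths. If times of death were exponential with that median (a further assumption), s = 1 − 0.5^(24/74) ≈ 20%.

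**4. Direction.** The early death rates and scores below are all assumed. Arm B has more early deaths than arm A.

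| Scenario | Survivors-only mean, A vs B | Death scored 0, A vs B |
|---|---|---|
| (i) Early deaths 9.6% vs 14.4%; A's survivors average 4.5; B's extra deaths would have scored 1 | 4.50 vs 4.70 | 4.07 vs 4.02 |
| (ii) 5% vs 10%; B's extra deaths would have scored 2; all other survivors score 5 | 4.84 vs 5.00 | 4.60 vs 4.50 |
| (iii) 5% vs 10%; survivors average 5 in both arms | 5.00 vs 5.00 | 4.75 vs 4.50 |

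Arithmetic for (i), per 100 babies: A totals 90.4 × 4.5 = 406.8. B totals 406.8 − 4.8 × 1 = 402.0 over 85.6 survivors, which is 4.70. With death as 0 the totals are divided by 100. For (ii): A is (0.05 × 2 + 0.90 × 5)/0.95 = 4.84, and with death as 0 it is 4.60; B with death as 0 is 0.90 × 5 = 4.50. For (iii): 0.95 × 5 = 4.75 and 0.90 × 5 = 4.50.

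In (i) and (ii) the arm with more deaths looks better. In (iii) the mean shows no difference. If in (i) the treatment also lowered survivors' scores by more than 4.696 − 4.500 = 0.196 points on average, the survivors-only mean would point the right way after all.

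**The case against.** The strongest reply is that an excess of early deaths would not be hidden. All-cause mortality is the primary outcome, time from start of procedures to death is a secondary outcome, and SAP 6.2 plans Cox regression and Kaplan-Meier curves. SAP 6.4.1 plans a first-24-hour analysis of heart rate and saturation, to which a baby who dies at 10 hours could contribute. SAP 6.5 compares serious adverse events by arm, and Protocol 8.3 counts severe instability among them. The safety board's interim look covered primary and secondary outcomes. All of this stands. A reader might infer that aSCRIP is the only safety evidence; the documents do not support that. What remains is that SAP 6.5 leaves death out of the adverse-event comparison, and no planned table sets deaths before 24 hours beside the 24-hour outcomes.

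Second, the outcome's wording is ambiguous. Protocol 6.1.1 has respiratory reviews every 6 hours, so the mean could be an average over the first day, and a baby who dies late in that day would have partial data. The SAP does not say so, and death would still carry no value.

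Third, scoring death as 0 has its own faults. A living baby can score 0, so death would tie with extreme instability. The score is also a pathway outcome under Objective 4, and building mortality into it blurs that use. In scenario (i) the death-inclusive difference is only about 0.05 points. These are good reasons not to make it the sole or main analysis, but not reasons to leave it out.

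**Conclusion.** The concern holds in limited form. As written, the plan yields survivors-only comparisons for aSCRIP and hypothermia at 24 hours without saying so. The aSCRIP comparison can show no difference, or a difference in favour of the arm with more early deaths; hypothermia loses the same babies and is open to the same problem. The primary outcome is unaffected.

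Two further inferences go beyond the documents. One is that the mean will move the wrong way. That requires the extra deaths to be babies who would have scored low, and the survivors' scores not to fall enough to offset it. The other is that more than 5% of scores will be missing. That depends on s exceeding about 12%, and the documents give no value for s. The feasibility timing rests on 14 deaths. Severely unstable babies are excluded, which should lower the share. The remark in SAP 2.1 about first-day deaths concerns preterm neonates in general, not this trial population. The range of about 4% to 12% is therefore conditional on s of 10% to 30% and on the planned mortality rates.

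**What to change.** In SAP 6.2 and 6.3:

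- State that the 24-hour aSCRIP and hypothermia analyses are among babies alive at 24 hours, and whether the score is a single reading or an average over the day.
- Tabulate deaths before the 24-hour reading, by arm, beside both outcomes.
- Pre-specify a supporting aSCRIP analysis that ranks death at or below the worst score, for example death = 0 or a rank-based comparison with death lowest. Ranking death strictly below 0 avoids the tie with living babies.
- Add a binary outcome, alive with temperature ≥36.5 °C at 24 hours, with death counted as failure.
- State that no safety conclusion will be drawn from the survivors-only mean if the death-inclusive analysis disagrees.

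This uses data already collected and costs some SAP wording, one small table and two supporting analyses. SAP 3.5 commits to posting the plan before the database closes and before any analyses, so the rule can be fixed without sight of the results. The downside is that a death-inclusive score mixes mortality with physiology, so it should be shown beside the survivors-only result and not replace it.
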